Enrollment will occur at the time the informed consent document is electronically signed. Following enrollment, each participant will be given a unique study ID to prevent duplicate enrollments. The study ID will consist of the patient's last initial, first initial, and the day they were born. The baseline study visit will occur immediately following enrollment and will consist of completing a baseline health questionnaire, counseling for HIV risk reduction, counseling for treatment of opioid use disorder (if applicable), point of care (POC) STI testing, POC HIV testing, offering oral PrEP for HIV risk reduction (if applicable), and offering buprenorphine for treatment of opioid use disorder (if applicable). All participants will also be offered laboratory-based STI testing of the oral and rectal sites. Participants who consent for PrEP will also have phlebotomy performed for serum creatinine, hepatitis B serologies, and a 4th generation HIV antigen/antibody assay. Clinic staff will also address any immediate medical concerns of the participant and treat as able per standard of care. At the enrollment study visit, each participant will be given a \$25 Visa gift card for their participation.

In addition to reimbursement for each study visit, participants will receive a financial incentive of \$15 for returning to receive any test results that required off-site lab testing, as is standard of practice at our community partner, Aurora Commons/SHE Clinic. Participants on buprenorphine will also receive \$15 each time they return for monthly refills. Financial incentives will be paired with low-barrier, walk-in care and adherence counseling at each visit.

Baseline study visit data collection

An electronic health questionnaire will be filled out by participants in REDCap using a clinic tablet. Research staff will be allowed to assist the participant in filling out the electronic health questionnaire, if the participant chooses. The questionnaire will assess for risk factors for HIV, PrEP eligibility, prior use of PrEP, history of substance use, prior use of medications for opioid use disorder (MOUD), and current use of MOUD. At the end of the study visit, each participant will complete a brief electronic survey in REDCap. This survey will assess the patient's overall experience receiving care at the venue-based clinic and assess the level of acceptability and perceived stigma associated with venue-based care.

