During or immediately following the visit, the clinic staff will fill out a visit summary report in REDCap, indicating the results of POC STI and HIV testing, any STI treatment given, if the participant was prescribed PrEP or reasons they were not prescribed PrEP, and if the participant was prescribed buprenorphine or reason the participant was not prescribed buprenorphine.

Follow-up study visits, Month 3 and Month 6 (Exit visit)

All patients will be asked to return to the clinic 3 months and 6 months following enrollment. At these follow-up study visits, patients will undergo additional counseling for HIV risk reduction

and treatment of opioid use disorder, as indicated based on their individual risk and substance use behaviors. At both the Month 3 and Month 6 visits, all patients will fill out a brief questionnaire self-reporting substance use and sexual behavior in the past three months. Participants who were previously prescribed PrEP through the venue-based clinic will fill out questions about their adherence to PrEP and barriers/facilitators to taking PrEP. Participants who were previously prescribed buprenorphine will similarly fill out questions about their adherence to buprenorphine and barriers/facilitators to taking buprenorphine. All participants who received a prescription for PrEP or buprenorphine will be asked to provide a 150-strand hair sample and a DBS sample for tenofovir and/or buprenorphine drug level checking. Any participant not previously initiated on PrEP or buprenorphine will be offered PrEP and/or buprenorphine at the follow-up study visits, as indicated per practice guidelines. Participants will be tested for STIs using POC testing, and any participant diagnosed with an STI will receive prompt treatment prior to leaving clinic, as outlined in the “Study Design: General Overview” section of this protocol. Additionally, participant will be offered laboratory-based STI testing of the oral and rectal sites. Participants who initiated PrEP will have phlebotomy performed for a 4th generation HIV antigen/antibody assay. Participants who did not initiate PrEP at baseline but initiate PrEP at month 3 or 6 will also have phlebotomy for serum creatinine and hepatitis B virus (HBV) serologies. Clinic staff will similarly address any immediate medical concerns of the participant, as per standard of care. At the end of each follow-up study visit, participants will be given a \$25 Visa gift card for their participation.

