All female identifying persons who present to the venue-based clinic will be eligible for receipt of HIV and STI testing, as well as oral PrEP and MOUD, regardless of participation in the research study. Similarly, study participants will be eligible for care if they visit the venue-based clinic for interim visits outside of their designated study visits (e.g., baseline, 3-months, 6-months, monthly refills for buprenorphine). Standard of care will include checking vital signs, addressing any immediate health concerns as able/feasible within the van clinic, laboratory-based HIV screening, laboratory-based STI testing, and prescription of oral PrEP and/or MOUD, though many services will require billing and insurance claims through the healthcare system and women will be made aware of these prior to initiating these services (e.g., laboratory-based testing, prescription drugs) (Table 1).

Table 1. Study Procedures					
Study Visit Month		0	3	6	Refill visits and Interim non-study visits
General Research Activities					
	Obtain informed consent	X			
	Screen for inclusion/exclusion	X			
	Collect updated contact information	X	X	X	X
	Reimbursement	X	X	X	
Research Questionnaires					
	Demographic information	X			
	Behavior (sexual and drug use and risk perception)	X	X	X	
	Adherence to PrEP and/or MOUD		X ^b	X ^b	
	Acceptability of venue-based care	X	X	X	
	Health and acute healthcare need	X	X	X	X
	Provider clinical summary report	X	X	X	X
Standard of care					
	Medication review	X	X	X	X
	General symptom assessment	X	X	X	X
	Blood pressure checks	X	X	X	X
	Supply condoms	X	X	X	X
	Contraception counseling and provision/referral	X ^{ab}	X ^{ab}	X ^{ab}	
	Laboratory Pregnancy testing	X ^{ab}	X ^{ab}	X ^{ab}	X ^{ab}
	Narcan prescription	X ^a	X ^a	X ^a	X ^{ab}
	Laboratory HIV test	X ^{ab}	X ^{ab}	X ^{ab}	X ^{ab}
	Laboratory STI (CT/GC and TV) genital testing	X ^{ab}	X ^{ab}	X ^{ab}	X ^{ab}
	Laboratory STI (CT/GC) pharyngeal and rectal testing	X ^{ab}	X ^{ab}	X ^{ab}	X ^{ab}
	Laboratory Syphilis testing (IgG and/or RPR)	X ^{ab}	X ^{ab}	X ^{ab}	X ^{ab}

	Laboratory Hepatitis B serologies	X ^{ab}			
	Laboratory Creatinine check	X ^{ab}		X ^{ab}	
	Laboratory Hepatitis C testing	X ^{ab}			X ^{ab}
	Suboxone prescription	X ^{ab}	X ^{ab}	X ^{ab}	X ^{ab}
	PrEP prescription	X ^{ab}	X ^{ab}	X ^{ab}	X ^{ab}
	STI treatment	X ^{ab}	X ^{ab}	X ^{ab}	X ^{ab}
	Referral to specialty care	X ^{ab}	X ^{ab}	X ^{ab}	X ^{ab}
Research Clinical Care					
	POC HIV/Syphilis testing (rapid test)	X	X	X	

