	POC Trichomonas screening (self-collected vaginal swab)	X	X	X	
	POC CT/NG testing (self-collected vaginal swab)	X	X	X	
	Hair sample collection (for TFV and Bupe levels)	X	X	X	
	Dried Blood Spot (for TFV and Bupe levels)	X	X	X	
	Financial Incentive for Returning for Results (following study visits)	X ^b	X ^b	X ^b	X ^b
^a only for those who consent to billing/insurance claim					
^b If clinically indicated					

Lab Processing and Results Delivery

Study specific labs will include hair sample and DBS collection for detection of tenofovir and buprenorphine levels, as well as self-collected vaginal swabs for POC STI testing and POC fingerstick HIV and syphilis testing.

Hair testing:

Hair samples will be sent to the Hair Analytical Laboratory (HAL) at the University of California San Francisco (UCSF-HAL). The HAL uses liquid chromatography-tandem mass spectrometry (LC-MS/MS) for testing. The HAL has found high rates of acceptability and feasibility (>95%) of collecting hair samples among U.S. adolescents and women. Our group has experience with hair collection across studies and has found it acceptable.

HAL will test hair sample for tenofovir and buprenorphine levels, as indicated based on medications prescribed to each participant. Results of hair sample testing will be used for research purposes only to determine adherence to prescribed medications, and results will not be returned to the individual participant.

DBS testing:

Dried blood spots will be obtained at baseline and at quarterly follow-up visits (Month 3 and Month 6) using a lancet finger stick to express drops of blood onto a 5-spot DBS card. This will be done following collection of a blood droplets from finger for the HIV/syphilis rapid test. The card will be labeled with participant ID and transported to PI's locked office where they will be securely stored for possible TFV and buprenorphine testing.

POC STI testing:

Chlamydia and Gonorrhea testing

Participants will give their self-collected vaginal swab specimen to clinic staff prior to survey completion. Participants will collect a vaginal swab in a private space in the study clinic. POC STI tests for *C. trachomatis* and *N. gonorrhoeae* will be available within 30 minutes using a small, FDA approved, CLIA waived PCR machine supplied by Binx Health. POC STI samples

will be processed in real time, with results delivered to participants during the study visit, and no samples stored.

Trichomoniasis testing

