Research Material Obtained from Participants

Individuals who are eligible and enroll in venue-based care will complete a baseline, 3-month and 6-month study visit. Data to be collected at those visits include information on demographics, risk factors for HIV, PrEP eligibility, prior use of PrEP, history of substance use, prior use of medications for opioid use disorder (MOUD), current use of MOUD, and self-reported adherence to PrEP and/or MOUD, as indicated. Participants will also provide information on their experience accessing venue-based care, including acceptability and perceived stigma associated with accessing venue-based care. POC HIV testing, POC STI testing, and standard of care labs for PrEP will be obtained at baseline, 3-months and 6-months. Hair samples and DBS samples to test for tenofovir and buprenorphine will be obtained at 3-month and 6-month visits. A review of the participants medical and pharmacy records will be conducted.

Assessment data will be collected directly onto iPads used by research team members. We will utilize the Research Electronic Data Capture (REDCap) system through the University of Washington's Institute of Translational Health Services (ITHS) to log and store data.

Women who are started on buprenorphine therapy will also return for monthly refill visits, during which time no additional study data will be collected.

Risks to Human Subjects

There are limited physical risks to study subjects beyond what is incurred during standard primary care. Participants may experience mild bruising or pain at the site of point of care finger prick testing (e.g., POC HIV and syphilis testing, DBS sampling), or at the site of phlebotomy draws. Participants who choose to initiate on oral PrEP and/or buprenorphine will be at risk of experiencing established side effects, as outlined in each drugs' prescribing materials.

Participants may experience psychological distress associated with discussing confidential topics such as sexual and drug use practices. Research medical team staff will be trained in trauma-informed care and to address psychological distress with a calm, non-judgmental attitude. We will take steps to minimize any psychological discomfort by ensuring confidentiality as described below. We will only enroll patients who understand the study procedures and are willing to participate.

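### Table 1 leaves blank three of the four creatinine and hepatitis B tests that the text requires for women who first start PrEP at Month 3 or Month 6

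*Protocol*

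**What the plan says.** Four places in the protocol bear on laboratory testing at PrEP start.

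- **Enrollment study visit.** Baseline testing is tied to accepting PrEP: "Participants who consent for PrEP will also have phlebotomy performed for serum creatinine, hepatitis B serologies, and a 4th generation HIV antigen/antibody assay".
- **Follow-up study visits, Month 3 and Month 6 (Exit visit).** Late starts are foreseen: "Any participant not previously initiated on PrEP or buprenorphine will be offered PrEP and/or buprenorphine at the follow-up study visits". For those women the section states: "Participants who did not initiate PrEP at baseline but initiate PrEP at month 3 or 6 will also have phlebotomy for serum creatinine". In full, the tests named are "serum creatinine and hepatitis B virus (HBV) serologies".
- **Table 1, Study Procedures.** The row "Laboratory Hepatitis B serologies" has a mark at Month 0 and nowhere else. The row "Laboratory Creatinine check" has marks at Month 0 and Month 6. The PrEP prescription row is marked in all four columns: Months 0, 3 and 6, and refill/interim visits. All these marks carry footnote a ("only for those who consent to billing/insurance claim") and footnote b (clinical indication).
- **Research Material Obtained from Participants.** This section says that "standard of care labs for PrEP will be obtained at baseline, 3-months and 6-months", without listing the tests.

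**The concern.** The follow-up section treats creatinine and hepatitis B serology as part of starting PrEP at a later visit, and its wording is unconditional. Table 1 allows the prescription at the same visits but does not schedule all the tests. A clinic session run from the table would test a late starter differently from one run from the text.

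The late start is a planned pathway. The Analysis Plan counts PrEP uptake from prescriptions accepted at baseline, Month 3 or Month 6. While the two places disagree, it also cannot be decided whether a missing test at a late start is a protocol deviation.

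**Working it through.** There is no figure in the plan to reproduce, so the check compares the text with the table cell by cell.

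**Inputs.** The required tests and visits come from the section on the Month 3 and Month 6 visits. The marks come from the hepatitis B, creatinine and PrEP prescription rows of Table 1.

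| Test | Visit at which PrEP is first started | Follow-up text | Table 1 |
|---|---|---|---|
| Serum creatinine | Month 3 | required | blank |
| Serum creatinine | Month 6 | required | marked (footnotes a, b) |
| Hepatitis B serologies | Month 3 | required | blank |
| Hepatitis B serologies | Month 6 | required | blank |
| PrEP prescription, for comparison | Months 3 and 6 | offered | marked at both (footnotes a, b) |

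**Count.** Cells required by the text: 2 tests × 2 visits = 4. Cells marked in Table 1: 1. Blank: 4 − 1 = 3.

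**By visit.** For a Month 3 start, the table marks 0 of the 2 required tests. For a Month 6 start, it marks 1 of 2. The table does not say whether the Month 6 creatinine mark is meant for new starters or continuing users. It is counted here as present, which is the reading more favorable to the table.

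**Can footnote b fill the blanks?** No. It qualifies cells that carry a mark. Other rows, such as the laboratory HIV and STI tests, use the same marked-with-footnotes form at later visits for conditional tests. A blank cell therefore reads as not scheduled.

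**Could the blanks come from reading the PDF?** This is unlikely. The neighboring hepatitis C row keeps its Month 0 and refill/interim marks with blanks between them, and the creatinine row keeps a blank between Months 0 and 6. The column positions appear to have survived.

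**Would baseline results already cover late starters?** Not under the enrollment text, which ties the baseline draw to women who accept PrEP then. Table 1 does allow the tests at Month 0 where clinically indicated, so some late starters may have had them. The protocol does not say how many.

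**The case against.** The strongest defense is that the text is explicit, a physician is on site, and PrEP is to be prescribed under clinical guidelines, so staff may well do the tests whatever the table shows. No section says that staff work from Table 1. This stands as a limit on the consequence: the protocol does not show that any test would in fact be missed. It does not remove the contradiction.

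A reader might infer more from these passages than they support.

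- **That Table 1 omits both tests at both visits.** It does not, because creatinine is marked at Month 6.
- **That footnote a lets a woman start PrEP without labs if she declines billing.** The PrEP prescription row carries the same footnote, so under the table she would receive neither the prescription nor the labs. The Standard of Care section also announces that laboratory tests and prescriptions may be billed. All that remains is that the enrollment and follow-up sections do not mention billing for these labs.
- **That interim visits show the same conflict.** Table 1 marks a PrEP prescription there and neither test, but no text sets a laboratory requirement for an interim start. The mark may also cover continuing prescriptions. This needs clarifying but is not a contradiction.
- **That the research-material section is a third, conflicting schedule.** It names no tests. The laboratory HIV assay is one of the PrEP labs and is marked at Months 0, 3 and 6, so the sentence can be read consistently with both other places.
- **That the DSMB would see incomplete safety data.** The DSMB Responsibilities section lists adverse events, serious adverse events and study conduct. It does not list creatinine or hepatitis B screening results.

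**Conclusion.** The contradiction between the follow-up text and Table 1 is real. Three of the four cells that the text requires for late PrEP starters are blank: both hepatitis B cells and creatinine at Month 3. Every late start, at either visit, has at least one required test that the table does not schedule at that visit.

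This rests on two assumptions: that the extracted table columns are in their true positions, and that a blank cell means not scheduled.

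The size is known in cells, not in women. The protocol gives no expected number of late starters among the 50 to be enrolled, and some may have been tested at baseline. No objective, denominator or analysis uses creatinine or hepatitis B results, so no statistical figure changes. The point matters because it concerns safety testing at the start of a medication, and it should be corrected.

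**What to change.** Reconcile Table 1 with the section on the Month 3 and Month 6 visits, and align the Enrollment study visit and Research Material Obtained from Participants sections, so that a single PrEP laboratory schedule applies at Months 0, 3 and 6. It would help if the research-material section named the tests it means. Which schedule is adopted is for the clinical leads; this review takes no view on it.

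Two secondary clarifications can go into the same amendment:

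- whether the schedule also covers PrEP first prescribed at an interim visit;
- how footnote a applies to these labs for enrolled women.

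The cost is a correction to a few table cells and matching sentences. No participants or study visits are added.

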Design: Pilot of novel care model for low-barrier care and adherence support for uptake and sustained use of biomedical HIV prevention and medications for opioid use disorder for women who inject drugs

Study Population: 50 female-identifying people ≥18 years of age and older who have ever injected drugs and are not known to be HIV-positive

Study Site: Community-based clinic on north Aurora Avenue in Seattle, WA

Primary Study Objectives:

1. Evaluate uptake of PrEP and MOUD
2. Evaluate sustained use of PrEP and MOUD
3. Evaluate treatment completion rate and time to completion after POC STI testing
4. Assess acceptability of pilot community-based care model
5. Assess acceptability of POC STI testing at community-based site.

Approach: We will conduct a pilot study of a community-based novel care model developed with community feedback and a community advisory board (CAB) co-design process during phase I of this project. We will enroll 50 female-identifying people and follow them for 6 months. We will assess uptake of PrEP and buprenorphine; POC STI testing and treatment completion rates; sustained use of PrEP and buprenorphine at months 3 and 6 (n=50). We will conduct surveys, guided by CFIR, to assess and characterize the acceptability and feasibility of venue-based primary and HIV prevention care among women who inject drugs (WWID).

Background and rationale

Women who inject drugs (WWID) experience frequent barriers to receiving primary care, especially sexual health and addiction services, because of perceived stigma, competing needs, and structural inequities within the healthcare system. Barriers to care among WWID are often exacerbated by the additional social chaos of unstable housing and engagement in transactional sex. These structural realities promote exclusion from traditional primary care systems, increase risk of HIV acquisition, and have led to rising rates of syphilis infections and overdose deaths among WWID in recent years. PrEP, buprenorphine, and STI control are key components of the End the HIV Epidemic prevention pillar and proven tools for reducing risk of HIV acquisition and opioid overdose, but uptake and sustained use of these interventions are low among WWID.

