Clinical study visits will occur at enrollment, a follow-up study visit at month-3, and an exit visit at 6-months post-enrollment. For participants who are prescribed buprenorphine, additional brief refill visits will occur at monthly intervals. All assessments will occur during in-person visits in the pilot clinic. Each study visit will consist of a short survey, an eligibility assessment for oral PrEP and MOUD, standard clinical care, and biological sample collections (i.e., DBS sample collection for research only, self-collected vaginal swabs for point-of-care STI testing, and blood samples for blood born infection testing). To test the impact of this pilot clinic model on improving uptake and sustained use of HIV prevention services, we will utilize medical record data and DBS drug (buprenorphine and tenofovir) levels. Prior to enrollment, participants will be asked to provide consent for participation in the study, review of electronic medical record (EMR) data, and review of pharmacy records. Consent will be collected using electronic data capture (REDCap) and participant data will be collected by medical record number (MRN) utilizing an EMR querying technology (Leaf) generated by the University of Washington as well as manual chart review. Participants meeting CDC eligibility criteria for PrEP will be counselled on HIV risk, offered HIV testing, and if negative and interested, oral PrEP will be prescribed per clinical guidelines. Additionally, participants with active self-reported use of opioids will be counselled on options for opioid use disorder treatment, and those interested in MOUD, will be provided with a prescription for buprenorphine-naloxone or buprenorphine, per clinical guidelines. Uptake of PrEP and buprenorphine will be measured by review of pharmacy and EMR records and will be defined by filling a prescription for PrEP or buprenorphine. In collaboration with [name] and the University of California San Francisco (UCSF) Hair Analytical Laboratory (HAL), we will measure sustained use of PrEP and buprenorphine via tenofovir disoproxil fumarate (TDF) and buprenorphine levels in samples of 150 hairs. The UCSF-HAL can simultaneously test for buprenorphine, fentanyl, and tenofovir from the same specimen, and we will measure these drug levels at 3- and 6- months to evaluate adherence to PrEP and buprenorphine. Additionally, dried blood spots (DBS) will be collected and archived to ensure that drug levels are collected during this study in the event there are any complications with hair testing.

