The DSMB will be responsible for reviewing and evaluating the study protocols, plans for participant safety, and data monitoring plan prior to study enrollment. The DSMB will also evaluate the study progress, including participant recruitment, enrollment, and retention, data collection, and general operations of the venue-based clinic. The DSMB will evaluate for treatment harm or benefit, including individual AEs and SAEs, and make decisions regarding the continuation, modification or termination of the study based on these data. The DSMB will also review external information, if relevant to the study, that might affect the ethics of study continuation (e.g., new therapeutic advances that impact standard of care).

Cadence of DSMB meetings

The DSMB will meet remotely with study MPIs:

1. Prior to enrollment
2. Once the study has reached 50% enrollment (n=25)
3. At least every 6 months thereafter while the study is active.

Following each meeting, the DSMB will make recommendations on continuation, modification, or termination of the study. Aside from these regular meetings, an unanticipated AE may prompt an ad hoc report to be distributed and may result in an ad hoc teleconference for the entire DSMB. Upon study completion no additional meetings will be required of the DSMB.

DSM Reporting

Following each meeting the DSMB will produce a report that will be sent to the UW IRB within 10 days and to NIDA within 30 days of the DSMB meeting. The report will include a meeting summary, DSMB recommendations regarding the continuation, modification, or termination of the research project, and any other specific recommendations put forth by the DSMB.

Analysis Plan

1. Evaluate uptake of PrEP:
 - a. Defined as the proportion of participants who accept a prescription for PrEP from the study team at any point (i.e., baseline, Month 3, and/or Month 6 visit) during study participation. The denominator will be all participants (N=50) enrolled in the study.
 - b. Participants who accept prescriptions for PrEP at multiple points throughout the study will only be counted once when calculating uptake.
 - c. Final analysis will present uptake as a percentage (proportion).
2. Evaluate uptake of MOUD
 - a. Defined as the proportion of participants who accept a prescription for MOUD from the study team at any point (i.e., baseline, Month 3, and/or Month 6 visit) during study participation. The denominator will be all participants (N=50) enrolled in the study.

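### Uptake of PrEP and MOUD is defined as a filled prescription in one section of the protocol and as an accepted prescription in another

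*Protocol*

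**What the plan says.** The first entry under Primary Study Objectives is "Evaluate uptake of PrEP and MOUD". The protocol then says twice how uptake is to be scored.

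- **Data Collection Overview:** "Uptake of PrEP and buprenorphine will be measured by review of pharmacy and EMR records", and it "will be defined by filling a prescription for PrEP or buprenorphine".
- **Analysis Plan, item 1a (PrEP):** "Defined as the proportion of participants who accept a prescription for PrEP from the study team at any point".
- **Analysis Plan, item 2a (MOUD):** "Defined as the proportion of participants who accept a prescription for MOUD from the study team at any point".

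Items 1a and 2a spell out the qualifying occasions in a parenthesis, "i.e., baseline, Month 3, and/or Month 6 visit) during study participation", and fix the denominator: "The denominator will be all participants (N=50) enrolled in the study". They mention neither filling nor pharmacy records.

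Two other places bear on which prescriptions count. Under Standard of Care, "study participants will be eligible for care if they visit the venue-based clinic for interim visits outside of their designated study visits", and Table 1 marks both PrEP and Suboxone prescription in the column for refill and interim non-study visits. Items 3a and 4a of the Analysis Plan restrict sustained use to participants prescribed the drug at an earlier study visit.

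**The concern.** Accepting a prescription and filling it are separate events. Table 1 footnotes PrEP and Suboxone prescriptions as available only to those who consent to billing or an insurance claim, so a prescription agreed to in the van need not become medication in hand. A participant who accepts and never fills is a success under the Analysis Plan and a failure under the Data Collection Overview.

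The study's main product is a small set of descriptive proportions. If the numerator of the first of them is not fixed, two analysts who both follow the protocol can report different results. A later reader comparing the figure with another programme would not know whether it measures willingness or possession.

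The list of visits raises a second, smaller question: whether a prescription first written at an interim visit counts at all.

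**Working it through.** **No figure to reproduce.** The protocol gives no expected uptake, fill rate, power or precision calculation for this objective. The check is a comparison of text, followed by an illustration of size.

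**Step 1: the two definitions side by side.**

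| | Data Collection Overview | Analysis Plan 1a, 2a |
|---|---|---|
| Event | prescription filled | prescription accepted |
| Source | pharmacy and EMR records | not stated |
| Prescriber | not restricted | study team |
| Occasion | not restricted | baseline, Month 3, Month 6 |

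For study-team prescriptions, every fill presupposes an acceptance but not the reverse, so acceptance is the easier criterion. Across all prescriptions neither definition contains the other: a fill of a prescription written elsewhere could count under the first and not under the second.

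**Step 2: illustrative size.** Let *a* be the proportion accepting and *f* the proportion of accepted prescriptions filled. If only study-team prescriptions matter, the gap is *a* - *a* × *f* = *a* × (1 - *f*).

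For *a*, use the uptake reported for the parent clinic in Background and rationale: 33% for PrEP and 49% for buprenorphine. That text does not say whether these are accepted or filled, so using them as acceptance is an assumption. The range *f* = 0.60 to 0.90 is also an assumption.

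- PrEP, *f* = 0.90: 33 × 0.10 = 3.3 points. *f* = 0.60: 33 × 0.40 = 13.2 points.
- Buprenorphine, *f* = 0.90: 49 × 0.10 = 4.9 points. *f* = 0.60: 49 × 0.40 = 19.6 points.

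For scale in whole participants, 17/50 accepting is 34%, with an exact (Clopper-Pearson) 95% interval of 21.2% to 48.8%. If 60% of those fill, 10/50 is 20% (10.0% to 33.7%). At the low end of the assumed fill range, the difference of 34 - 20 = 14 points is about half the width of the first interval ((48.8 - 21.2)/2 = 13.8). The choice of definition could then matter as much as sampling error.

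**Step 3: interim visits.** Read literally, the parenthesis in items 1a and 2a lists three visits and no others.

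- First prescribed at an interim visit, accepts again at Month 3 or Month 6: counted.
- Prescribed at an interim visit only: not counted.

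Each participant of the second kind moves the proportion by 1/50 = 2 percentage points. Their number is unknown and may be small. Under items 3a and 4a, an interim starter stays out of the sustained-use denominator until she is prescribed at a study visit. One who starts before Month 3 cannot contribute at Month 3; if prescribed at Month 3, she enters at Month 6.

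**The case against.** The best defence is that the Analysis Plan is specific and computable. It names an event, the occasions and a denominator; staff record at each study visit whether each drug was prescribed; and actual exposure is assessed separately through drug levels. In a 50-person single-group pilot with no test or decision threshold on uptake, an analyst would probably follow it. All of that is fair, but no order of precedence is stated, and the other definition is equally explicit and names its own data source. The conflict stands.

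Four stronger readings are tempting, and the protocol does not support them.

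- *Every interim starter is scored as no uptake.* Not so: she is counted if she accepts again at Month 3 or Month 6. The point also needs a strict reading of the parenthesis. If the visits were meant as examples, it falls away for uptake, though the wording of items 3a and 4a would remain.
- *The poor follow-through reported at the parent clinic is the gap between accepting and filling.* Background and rationale describes high initial uptake and then low sustained use (0-5% for PrEP and 12% for buprenorphine after six months). The known loss comes after uptake. There is no evidence on fill rates in either direction.
- *Acceptance must overstate uptake.* Not certain, since fills from other prescribers could count under the filling definition.
- *The definition was changed after data were seen.* Some later items of the Analysis Plan are in the past tense, but items 1 and 2 show no sign of a change.

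**Conclusion.** The protocol is wrong as written on this point: its first-listed primary objective has two incompatible numerators and nothing to choose between them. That conclusion rests on the text alone.

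The size is not known. About 3-13 points for PrEP and 5-20 for buprenorphine is an illustration that depends on three assumptions: acceptance equal to the parent clinic's uptake, 60-90% of prescriptions filled, and no fills from outside prescribers. The consequence is an ambiguous descriptive result, not a faulty test, because no test is planned.

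The omission of interim-visit prescriptions is secondary. It affects uptake only for participants with no later study-visit prescription, and only if the parenthesis is read as exhaustive.

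**What to change.** Put one definition in both the Data Collection Overview and Analysis Plan items 1a and 2a. For example: uptake is at least one PrEP (or buprenorphine) prescription written by the study team and filled, according to pharmacy and EMR review. State a fill window for prescriptions issued at the Month 6 visit, so that a fill shortly after exit is handled the same way for everyone. Report the proportion accepting a prescription alongside it, with the same denominator of all enrolled.

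State that prescriptions from interim and refill visits count. In items 3a and 4a, replace the condition of an earlier study visit with any preceding visit.

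The cost is a wording amendment and some record review, for which participant consent is already planned. The reported uptake may come out lower than under acceptance alone.
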